Objective: The infection caused by the severe acute respiratory syndrome coronavirus 2 (SARS-CoV2) spreads worldwide and is considered a pandemic. The most common manifestation of SARS-CoV2 infection (Coronavirus disease 2019 - COVID-19) is viral pneumonia with varying degrees of respiratory compromise and up to 40% of hospitalized patients might develop acute respiratory distress syndrome. Several clinical trials evaluated the role of corticosteroids in non-COVID-19 acute respiratory distress syndrome with conflicting results. We designed a trial to evaluate the effectiveness of early intravenous dexamethasone administration on the number of days alive and free of mechanical ventilation within 28 days after randomization in adult patients with moderate or severe acute respiratory distress syndrome due to confirmed or probable COVID-19.

Methods: This is a pragmatic, prospective, randomized, stratified, multicenter, open-label, controlled trial including 350 patients with early-onset (less than 48 hours before randomization) moderate or severe acute respiratory distress

syndrome, defined by the Berlin criteria, due to COVID-19. Eligible patients will be randomly allocated to either standard treatment plus dexamethasone (intervention group) or standard treatment without dexamethasone (control group). Patients in the intervention group will receive dexamethasone 20mg IV once daily for 5 days, followed by dexamethasone 10mg IV once daily for additional 5 days or until intensive care unit discharge, whichever occurs first. The primary outcome is ventilator-free days within 28 days after randomization, defined as days alive and free from invasive mechanical ventilation. Secondary outcomes are all-cause mortality rates at day 28, evaluation of the clinical status at day 15 assessed with a 6-level ordinal scale, mechanical ventilation duration from randomization to day 28, Sequential Organ Failure Assessment Score evaluation at 48 hours, 72 hours and 7 days and intensive care unit -free days within 28.

Keywords: Coronavirus; Respiratory distress syndrome, adult; Adrenal cortex hormones; COVID-19; Critical care; Dexamethasone

ClinicalTrials.gov identifier: NCT04327401.

INTRODUCTION

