- Change in the Sequential Organ Failure Assessment (SOFA) Score 48 hours, 72 hours and 7 days after randomization

Time schedule and study duration

The planned study duration is five months, being three months of recruitment, one month of follow up and one month for data analysis and manuscript writing. The first patient was enrolled on April 17th. The final report and publication are expected to be available on the second half of 2020.

Eligibility criteria

We will include critically ill patients with ARDS due to confirmed or probable COVID-19 admitted to the ICU. Probable COVID-19 is defined by the presence of symptoms, which are contemplated in the inclusion criteria, travel or residence in a city where community transmission is reported or contact with a confirmed case in the last 14 days prior symptoms onset⁽¹⁹⁾ and radiological imaging findings compatible with COVID-19 at the time of inclusion.

After 182 patients have been enrolled, the Steering Committee suggested specific changes on both inclusion and exclusion criteria. The timing of ARDS diagnosis for inclusion changed from 24 hours to 48 hours. The rationale for this modification was due to most centers receiving patients intubated in the ICU already with ARDS diagnosis and more than 24 hours of mechanical ventilation, which shortened the time window for recruitment. Additionally, given the widespread use of corticosteroids before ICU admission in Brazil, we allowed inclusion of patients who have previously received one day of corticosteroids during hospital stay, which was not allowed at first. The exclusion criteria were refined by adding three more criteria: use of immunosuppressive drugs, cytotoxic chemotherapy in the past 21 days, and neutropenia due to hematological or solid malignancies with bone marrow invasion.

Each patient must fulfil all the following inclusion criteria to be eligible for enrolment:

- Age ≥ 18 years old
- Probable or confirmed infection by SARS-CoV2
- Intubated and mechanically ventilated
- Moderate or severe ARDS according to Berlin criteria⁽²⁰⁾ (Table 2)

- Onset of moderate or severe ARDS in less than 48 hours before randomization

Exclusion criteria are:

- Pregnancy or active lactation
- Known history of dexamethasone allergy
- Daily use of corticosteroids in the past 15 days
- Indication for corticosteroids use for other clinical conditions (e.g refractory septic shock)

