Adherence to protocol and corticosteroids use in both groups is accessed daily. The use of corticosteroids in the control group is not forbidden since critically ill patients might have another

indication for corticosteroid use during their ICU stay. However, any use of corticosteroids for treating ARDS and or refractory hypoxemia in the control group is considered protocol deviation. Changes in dosage of dexamethasone or early interruption in the intervention group will also be considered protocol deviation.

If during the trial the patient is deemed to not have COVID-19 infection, which is defined by a negative laboratory tests along with negative evaluation by the Adjudication Committee, the study drug will be stopped, data on these patients will be collected until day 28 and will be included in the final analysis. However, giving the epidemiological context and inclusion criteria, it is expected that only a minority of patients will be in this group.

All centers will receive an initial training session before initiating recruitment to ensure consistency of the study procedures and data collection.

Data collection and management

Unidentified patient data will be collected through an electronic online data capture tool (REDCap).^(22,23) Demographic and baseline data, height, Simplified Acute Physiology Score (SAPS) 3, use of corticosteroids prior the randomization, and the HScore for diagnosis of secondary hemophagocytic lymphohistiocytosis (Table 3) are collected for all patients. The SOFA score is collected on days 1, 2, 3 and 7. Data from gas exchange, lung mechanics, hemodynamic, laboratory data, use of neuromuscular blocking agents, prone positioning and use of ECMO are collected prior randomization and until day 14.

The use of mechanical ventilation or any other ventilation/oxygen support (high flow nasal cannula, non-invasive ventilation, use of supplementary oxygen) and data on the 6-point Ordinal Scale (Table 1) are collected daily until day 28 or until hospital discharge whichever comes first. Vital status at ICU and hospital discharge and any other relevant clinical data such as nosocomial infections, insulin use for glycemic control, antibiotic use, and other therapies for COVID-19 (hydroxychloroquine, chloroquine and azithromycin) are collected.

Data on mechanical ventilation are collected in specific forms with data on date and time of initiation and discontinuation of therapy.

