The primary objective is to evaluate the effectiveness of early intravenous (IV) dexamethasone administration in ventilator-free days at 28 days after randomization, defined as alive and free from mechanical ventilation in adult patients with moderate or severe ARDS due to confirmed or probable SARS-CoV2 infection. Patients discharged from the hospital alive before 28 days will be considered alive and free from mechanical ventilation at day 28. Number of days free from mechanical ventilation will be presented as mean and standard deviation. The treatment effect will be presented as mean difference, with 95% confidence interval and P-value. We will use a generalized linear model with beta-binomial distribution or zero/one inflated beta distribution, with center as random effect and adjusted for age, corticosteroid use before randomization and PaO₂/FiO₂ ratio.

All-cause mortality rates at 28 days will be analyzed using a mixed Cox model, with centers as random effects (frailty model). The treatment effect on SOFA Score 48h, 72h, and 7 days after randomization will be analyzed by a linear mixed model with centers as random effects. For the clinical status of patients, an ordinal logistic regression will be used. The results will be presented as a proportional odds ratio comparing two combinations: Intervention versus Control. The probability ratios will be derived from a mixed logistic regression of proportional probabilities adjusted for age and PaO₂/FiO₂ ratio, with random intercepts for the center. The cumulative ordinal scores will be presented separately, as well as the main secondary results. Each odds ratio will be estimated using mixed logistic regression. The same models will be used to compare the effects of treatment on the follow-up. In case of the proportional odds assumption is not met, categories of the Ordinal scale 1-4 will be grouped as a single category for the analysis. All secondary outcomes are exploratory and no adjustment for multiple testing will be made.

Adverse events will be expressed as counts and percentages and compared between groups using the Chi-square test. The main results will be displayed as the supplementary table 2 (**Table 2S**). The significance level for all analyses will be 0.05. There will be no adjustment for multiple testing. All analyses will be performed using the R software⁶ (R Core Team, Vienna, Austria, 2020).

Table 2S - Main results presentation

Outcomes	Dex.	Cont.	Treatment effect	

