	n = xxx	n = xxx	Dex. versus Cont. [IC95%]	p valor
Primary outcome				
Ventilator free days from 1 to 28 d, mean (SD)	xx.x ± xx.x	xx.x ± xx.x	x.xx [x.xx; x.xx]	x.xx
Secondary outcomes				
Clinical status at day 15, N (%)				
Category 1 - 5 versus 6 (alive vs dead)	x.xx (x.xx)	x.xx (x.xx)	x.xx [x.xx; x.xx]	x.xx
Category 1 - 4 versus 5 - 6	x.xx (x.xx)	x.xx (x.xx)	x.xx [x.xx; x.xx]	x.xx
Category 1 - 3 versus 4 - 6	x.xx (x.xx)	x.xx (x.xx)	x.xx [x.xx; x.xx]	x.xx
Category 1 - 2 versus 3 - 6	x.xx (x.xx)	x.xx (x.xx)	x.xx [x.xx; x.xx]	x.xx
Category 1 versus 2 to 6 (at home versus hospital or dead)	x.xx (x.xx)	x.xx (x.xx)	x.xx [x.xx; x.xx]	x.xx
All-cause mortality at 28 days	x.xx (x.xx)	x.xx (x.xx)	x.xx [x.xx; x.xx]	x.xx
Number of days of MV from 1 to 28 d	x.xx (x.xx)	x.xx (x.xx)	x.xx [x.xx; x.xx]	x.xx
ICU free days at 28 days	x.xx (x.xx)	x.xx (x.xx)	x.xx [x.xx; x.xx]	x.xx
SOFA scores				
48 hours	x.xx (x.xx)	x.xx (x.xx)	x.xx [x.xx; x.xx]	x.xx
72 hours	x.xx (x.xx)	x.xx (x.xx)	x.xx [x.xx; x.xx]	x.xx
7 days	x.xx (x.xx)	x.xx (x.xx)	x.xx [x.xx; x.xx]	x.xx
Adverse events				
New diagnosis of infection until day 28, N (%)	x.xx (x.xx)	x.xx (x.xx)	x.xx [x.xx; x.xx]	x.xx
Insulin use for hyperglycemia, N (%)	x.xx (x.xx)	x.xx (x.xx)	x.xx [x.xx; x.xx]	x.xx

Sensitivity analyses

We plan to perform analyses to assess treatment effects on the primary and secondary outcomes considering only patients that received the proposed treatment in the intervention group and patients that not received corticosteroids in the control group (per protocol analysis). Additionally, we will also perform sensitivity analysis for the primary outcome in the following groups:

1. Confirmed COVID-19 infection
2. Confirmed and probable COVID-19 infection
3. Patients which received corticosteroids and patients which did not received corticosteroids (as treated analysis)
4. Patients which received the proposed treatment in the intervention group and patients that not received corticosteroids in the control group (Per protocol analysis)

Subgroup analyses

Will also perform subgroup analysis adding an interaction parameter with group in the main model for (Table 3S):

1. Age, years (< 60 and ≥ 60)
2. PaO₂/FiO₂ ratio, mmHg (≤ 100 and >100)
3. SAPS3, points (< 50 and ≥ 50)
4. Duration of symptoms at randomization, days (≤ 7 and > 7)
5. Duration of moderate / severe ARDS to randomization, hours (≤ 24 hours and > 24 hours to 48 hours)
6. Position at randomization; (prone or supine)
7. HScore (≥ 169 and < 169)

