Appendix 4 - Data Monitoring Committee (DMC) Charter Version 1.1. June 10th, 2020

Content	Charter details
Introduction	
Name of the trial	COVID-19-associated ARDS treated with DEXamethasone: CoDEX Trial Trial Intervention Intravenous dexamethasone
Objectives	Primary objective 1. Evaluate the effectiveness of early intravenous (IV) dexamethasone administration in ventilator-free days at 28 days after randomization in adult patients with moderate or severe ARDS due to confirmed or probable SARS-CoV2 infection Secondary objectives 1. All-cause mortality rates at 28 days after randomization 2. Clinical status of patients at 15 days after randomization using the 6-point Ordinal Scale 3. Number of days of mechanical ventilation from randomization to day 28 4. ICU free days at day 28 5. Change in the Sequential Organ Failure Assessment (SOFA) Score 48h, 72h and 7 days after randomization
Outline of scope of charter	The purpose of this document is to describe the membership, terms of reference, roles, responsibilities, authority, decision-making of the DMC for the CoDEX Trial, including the timing of meetings, methods of providing information to and from the DMC, frequency and format of meetings, statistical issues and relationships with other committees
Roles and responsibilities	
A broad statement of the aims of the committee	To protect and serve the CoDEX Trial patients regarding safety and to assist and advise the Academic Steering Committee to protect the validity and credibility of the CoDEX Trial. To safeguard the interests of the CoDEX Trial participants, assess the safety and efficacy of the interventions during the trial, and monitor the overall conduct of the CoDEX Trial.
Terms of reference	The DMC should receive and review the progress and accruing data of the CoDEX Trial and provide advice on the conduct of the trial to the Academic Steering Committee. The DMC should inform the Academic Steering Committee if, in their view: 1. The results are likely to convince a broad range of clinicians, including those supporting the trial and the general clinical community, that one trial arm, or a subset of trial population, is clearly indicated or contraindicated, and there was a reasonable expectation that this new evidence would materially influence patient management.

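### The SOFA outcome is stated as a change, but the SAP models levels without a baseline SOFA, and the text schedule does not identify a pre-randomization score

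*Combined protocol and SAP*

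**What the plan says.** The last item in the protocol's list of secondary objectives is "Change in the Sequential Organ Failure Assessment (SOFA) Score 48 hours, 72 hours and 7 days after randomization". The DMC charter (Appendix 4, Objectives) has the same outcome: "Change in the Sequential Organ Failure Assessment (SOFA) Score 48h, 72h and 7 days after randomization". The abstract is looser and speaks of "Sequential Organ Failure Assessment Score evaluation at 48 hours, 72 hours and 7 days", which is a level rather than a change.

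The only SOFA schedule in the text is in the protocol under Data collection and management: "The SOFA score is collected on days 1, 2, 3 and 7". Day 1 is not defined there. The next sentence covers gas exchange, lung mechanics, hemodynamic and laboratory data, among other items, and says that these "are collected prior randomization and until day 14". SOFA is not in that list.

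The SAP (Appendix 3) says "The treatment effect on SOFA Score 48h, 72h, and 7 days after randomization will be analyzed by a linear mixed model", with center as the random effect. It names no change score and no baseline SOFA for this model. Table 2S reports SOFA scores at 48 hours, 72 hours and 7 days. Table 1S, the baseline table, has no SOFA row.

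**The concern.** A change from baseline needs four values per patient: one at or before randomization, and one each at 48, 72 and 168 h. The text does not say which collected score is the baseline, and the planned model does not use one. The protocol and charter therefore name one quantity and the SAP analyses another.

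Two things are at stake. First, whether the outcome is a change or a level, and which score would count as baseline, is left open until the data are in hand. In an open-label trial that is better settled beforehand. Second, a model without baseline SOFA leaves between-patient differences in initial organ dysfunction in the residual variance. The SAP names covariates elsewhere: age, prior corticosteroid use and PaO₂/FiO₂ for the primary outcome, and age and PaO₂/FiO₂ for the ordinal scale. None is named for SOFA.

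**Working it through.** The plan gives no figure to reproduce here. The check maps collection days to hours and compares the result with what the objective needs.

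**Inputs.** Required times, from the secondary objectives: 0 h or earlier, 48 h, 72 h and 7 × 24 = 168 h. Collection days, from Data collection and management: 1, 2, 3 and 7.

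**Mapping under three uniform conventions**

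| Convention | Day 1 | Day 2 | Day 3 | Day 7 | What is lacking |
|---|---|---|---|---|---|
| Day 1 is the moment of randomization, hours = 24(d − 1) | 0 h | 24 h | 48 h | 144 h | 72 h score; day 7 is 168 − 144 = 24 h early |
| Hours = 24d | 24 h | 48 h | 72 h | 168 h | Any score at or before 0 h |
| 24 h windows, day 1 is 0–24 h | 0–24 h | 24–48 h | 48–72 h | 144–168 h | Day 1 lies after randomization; the later windows end at 48, 72 and 168 h |

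**Why shifting the origin does not help.** The gaps between required times are 48 − 0 = 48, 72 − 48 = 24 and 168 − 72 = 96 h. The gaps between collection days are 24, 24 and 4 × 24 = 96 h. The first gaps differ, so no constant offset fits all four points.

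**A convention that would fit.** If the day-1 score is taken before the first dose and days 2, 3 and 7 are scored at the end of their 24 h windows, all four values exist. The text neither states nor excludes this.

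**Precision from a baseline covariate.** With correlation r between baseline and follow-up SOFA, adjustment multiplies the variance of the treatment contrast by about 1 − r². The documents give no r; 0.5 to 0.7 is an assumption.

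- r = 0.5: 1 − 0.25 = 0.75, a 25% reduction, equivalent to 1/0.75 = 1.33 times the patients.
- r = 0.7: 1 − 0.49 = 0.51, a 49% reduction, equivalent to 1/0.51 = 1.96 times the patients.

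**The case against.** The strongest reply is that the planned analysis works as written. The protocol refers to the SAP for secondary outcomes, and the SAP compares levels. Under randomization, the between-arm difference in level has the same expectation as the difference in change from a pre-randomization score. Chance imbalance in initial severity is not bias, and the confidence interval already reflects it. This stands: the model needs no baseline to be valid. The remaining loss is precision, plus the disagreement between documents.

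A reader might infer that the schedule cannot supply the outcome at all. The documents do not support that. The protocol places the study timeline in Figure 2, which was not available for this review and may define day 1 or show a separate baseline SOFA. The mixed convention described above would also work. Table 2S counts follow-up from day 1 to day 28, which makes 24 h study days ending at 48, 72 and 168 h a natural reading. Only the timing of the day-1 score relative to the first dose would then be open. Even under the least favorable numbering, the 7-day score is one day early, not absent.

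A reader might also infer that part of the treatment effect will be subtracted by using a post-dose day-1 score as baseline. No document plans that subtraction. It is a risk to rule out in the wording, not a flaw in the stated analysis.

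Finally, SOFA is one of five secondary outcomes, all labelled exploratory in the SAP, and no sample size or stopping rule rests on it. That limits the weight of the point.

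**Conclusion.** The point holds in a limited form. The protocol objectives and the charter state a change in SOFA; the SAP analyses levels without a baseline SOFA. The text schedule does not identify a pre-randomization score, and no uniform day numbering yields a baseline together with all three follow-up times. That last statement is conditional: Figure 2 or an unstated mixed convention may resolve it. If Figure 2 did, the change-versus-level difference between protocol, charter and SAP would still remain.

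The consequence is lost precision on an exploratory secondary outcome and an avoidable ambiguity about what is estimated. The variance reduction of about 25% to 49% depends wholly on the assumed correlation of 0.5 to 0.7. Neither the primary analysis nor the validity of the planned between-arm comparison is in question.

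**What to change.** Before database lock:

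1. State in the protocol, SAP and charter how study days map to hours after randomization, and which scores represent 48 h, 72 h and 7 days.
2. Use the day-1 SOFA as baseline only where it was scored before the first dose. Otherwise derive a baseline SOFA from the gas exchange, hemodynamic and laboratory values already collected before randomization, with chart lookup for any missing component (the neurological item, for instance). Do not use a post-dose day-1 score as baseline.
3. Analyse SOFA at 48 h, 72 h and 7 days in the planned mixed model, adding that baseline as a covariate. Describe the outcome once, in the same words, in all three documents.

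The cost is wording changes and some back-calculation. The latter is not trivial: the protocol reports 182 of the planned 350 patients enrolled before the eligibility changes, and collection times for patients already enrolled cannot be altered. Where their scores do not fall at the stated hours, the SAP should give the actual timing. Treatment, sample size and the primary analysis are unaffected.

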 29. R Foundation for Statistical Computing. R: A language and environment for statistical computing [program]. Vienna, Austria: R Foundation for Statistical Computing; 2019.

Table 1 - The 6-point Ordinal Scale

1	Not hospitalized.
2	Hospitalized, not requiring supplemental oxygen.
3	Hospitalized, requiring supplemental oxygen.
4	Hospitalized, requiring non-invasive ventilation or nasal high-flow oxygen therapy
5	Hospitalized, requiring invasive mechanical ventilation or ECMO
6	Death

ECMO - extracorporeal membrane oxygenation.

Table 2 - Berlin Criteria for ARDS diagnosis

Timing	Within one week of a known clinical insult or new or worsening respiratory symptoms
Chest imaging	Bilateral opacities – not fully explained by effusions, lobar/lung collapse, or nodules
Origin of edema	Respiratory failure not fully explained by cardiac failure or fluid overload
Oxygenation	
Moderate	100mmHg < PaO ₂ /FiO ₂ ≤ 200mmHg with PEEP ≥ 5cmH ₂ O
Severe	PaO ₂ /FiO ₂ ≤ 100mmHg with PEEP ≥ 5cmH ₂ O

PaO₂/FiO₂ - partial pressure of oxygen/fraction of inspired oxygen, PEEP - positive end-expiratory pressure.

Table 3 - HScore for diagnosis of secondary hemophagocytic lymphohistiocytosis

Variable	Number of points
Temperature (°C)	
< 38.4	0
38.4 to 39.4	33
>39.4	49
Organomegaly	
No	0
Spleen or liver	23
Spleen AND liver	38
Number of cytopenia	
1 lineage	0
2 lineages	24
3 lineages	34
Triglyceride (mg/dL)	
< 133	0
133 to 354	44
> 354	64
Fibrinogen (g/dL)	
> 2.5	0
< 2.5	30
Ferritin	
< 2000	0
2000 to 6000	35
> 6000	50
Aspartate transaminase (AST) (U/L)	
< 30	0
≥ 30	19
Hemophagocytosis features on bone marrow aspirate	
No	0
Yes	35
Known immunosuppression	
No	0
Yes	18

[figure not shown]

Figure 1 - Study diagram. ARDS - acute respiratory distress syndrome; ICU - intensive care unit.

[figure not shown]

Figure 2 - Study timeline. ICU - intensive care unit; MV - mechanical ventilation.

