Two interim analyses are planned for safety and efficacy evaluation, after 96 patients and 234 patients with the complete follow up to the primary outcome. Based on the results of these interim analyses, the DMC will decide if there is proof beyond a reasonable doubt that the intervention is effective or not safe in this population. The stopping rule for safety will be a p-value $<$ 0.01 and for efficacy p-value $<$ 0.001 (Haybittle–Peto boundary). The Haybittle–Peto boundary is a conservative stopping rule at interim analysis that has minimal impact in increasing type I error in two-arm trials.⁽²⁸⁾ The interim analyses will be performed by an external and independent DMC.

Statistical methods

Main analyses will follow the intention-to-treat principle. For the primary outcome, a generalized linear model will be built with beta-binomial distribution or zero/one inflated beta distribution, with center as random effect and adjusted for age, corticosteroid use before randomization and PaO₂/FiO₂ ratio. The effect size will be estimated as mean difference, the respective 95% confidence interval, and hypothesis testing. Missing data on the primary outcome will be dealt with using multiple imputation techniques.

For details regarding the analysis of the secondary outcomes and other analysis, please refer to the Statistical Analysis Plan (SAP) on the appendix 3 of the supplementary material.

The significance level for all analyses will be 0.05. There will be no adjustment for multiple testing. All analyses will be performed using the R software⁽²⁹⁾ (R Core Team, Vienna, Austria, 2020).

Subgroup and sensitivity analyses

We plan to perform subgroup analysis for the primary endpoint, including interaction parameters in the main model to:

- Age (< 60 and \geq 60)
- PaO₂/FiO₂ ratio (\leq 100 and > 100)
- SAPS3 (< 50 and \geq 50)
- Duration of symptoms at randomization, days (\leq 7 and > 7)
- Duration of moderate / severe ARDS to randomization, hours (\leq 24 hours and > 24 hours to 48 hours)
- Position at randomization; (prone or supine)
- HScore⁽³⁰⁾ (\geq 169 and < 169)
- Use of corticosteroids before randomization
- Use of vasopressors at randomization

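### The HScore scoring table prints the fibrinogen cut-off as 2.5 g/dL (25 g/L); read literally, that item gives everyone 30 points and cannot separate patients

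*Combined protocol and SAP*

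**What the plan says.** The protocol's Data collection and management section states that "HScore for diagnosis of secondary hemophagocytic lymphohistiocytosis (Table 3) are collected for all patients". Table 3 is thus the only definition of the score in the documents. Its fibrinogen row is headed "Fibrinogen (g/dL", closing bracket omitted here, with two levels: above 2.5 scores 0 and below 2.5 scores 30. A value of exactly 2.5 belongs to neither level. The ferritin row, worth up to 50 points, has no unit.

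The score is used in two places:

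- **Baseline.** SAP Table 1S reports the number and percentage of patients with HScore ≥ 169 in each arm.
- **Subgroup.** The SAP's Subgroup analyses section lists "HScore (≥ 169 and < 169" as item 7 of nine, and Table 3S has rows for it. The protocol has the same split under Subgroup and sensitivity analyses, introduced by "We plan to perform subgroup analysis for the primary endpoint, including interaction parameters in the main model to" the nine listed factors.

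The documents give no fibrinogen reference range, no second statement of the unit, no unit for the eCRF field and no scoring algorithm.

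**The concern.** A two-level scoring item is useful only if patients can fall on either side of its cut-off. A cut-off of 2.5 g/dL looks roughly ten times too high for plasma fibrinogen, which suggests that the unit label is wrong. If the table is applied as printed, the item adds the same 30 points for everyone, and the 169 threshold no longer means what the plan intends.

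The HScore split is the listed subgroup that corresponds to the hyperinflammation rationale in the Introduction, where severe COVID-19 is likened to secondary hemophagocytic lymphohistiocytosis. If patients are put in the wrong stratum, the baseline row and the interaction estimate describe a different group from the one named. The protocol also plans to share data for individual-patient meta-analysis and to release the dataset publicly, so a wrongly derived variable could travel beyond this trial.

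**Working it through.** **Inputs from Table 3.** Points available per item:

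- temperature 0/33/49
- organomegaly 0/23/38
- cytopenia 0/24/34
- triglyceride 0/44/64
- fibrinogen 0/30
- ferritin 0/35/50
- AST 0/19
- marrow hemophagocytosis 0/35
- immunosuppression 0/18

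The threshold of 169 comes from the protocol and the SAP.

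**Assumption.** Plasma fibrinogen lies within 100 to 1,500 mg/dL (0.1 to 1.5 g/dL, 1 to 15 g/L). The documents do not give this range; it is deliberately wide.

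**Step 1, unit conversion.** 1 g/dL = 10 g/L = 1,000 mg/dL, so 2.5 g/dL = 25 g/L = 2,500 mg/dL. If the number 2.5 were in g/L, the cut-off would be 0.25 g/dL = 250 mg/dL.

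**Step 2, points for the fibrinogen item under three ways of applying the row.**

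| Fibrinogen (mg/dL) | As printed, g/dL | 2.5 read as g/L | Raw mg/dL number compared with 2.5 |
|---|---|---|---|
| 100 | 30 | 30 | 0 |
| 200 | 30 | 30 | 0 |
| 250 | 30 | unassigned | 0 |
| 300 | 30 | 0 | 0 |
| 400 | 30 | 0 | 0 |
| 1,000 | 30 | 0 | 0 |
| 1,500 | 30 | 0 | 0 |

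Only the g/L reading separates patients. The as-printed result would change only for values of 2,500 mg/dL or more, so it does not depend on the exact limits of the assumed range.

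**Step 3, effect on the threshold.** The maximum total is 337, of which 307 comes from the other eight items (49 + 38 + 34 + 64 + 50 + 19 + 35 + 18). With a constant 30 points, the total reaches 169 once the other items reach 169 − 30 = 139. Relative to the g/L reading, a patient changes group only if fibrinogen is not low and the other items total 139 to 168. Patients with truly low fibrinogen receive the 30 points under both readings.

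**Step 4, an example.** Temperature 38.4 to 39.4 (33), triglyceride 133 to 354 (44), ferritin above 6000 (50) and AST of at least 30 (19) total 146. With non-low fibrinogen the score is 146 under the g/L reading, below 169. As printed it is 146 + 30 = 176, in the high group.

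**Step 5, enumeration of possible score patterns.**

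- Without marrow or immunosuppression points there are 3 × 3 × 3 × 3 × 3 × 2 = 486 patterns. With 0 fibrinogen points 145 reach 169; with 30 points 258 do. The difference, 258 − 145 = 113, switch group.
- With those two items included there are 486 × 2 × 2 = 1,944 patterns. The counts are 984 and 1,395, so 411 switch.

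Each pattern counts once, however common or rare it is in practice, so these counts show that the threshold is sensitive to the item. They do not estimate a share of patients.

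**The case against.** A reader might infer that every enrolled patient was given 30 points and that the HScore ≥ 169 group is inflated. The documents do not support that. It would require values to have been scored in g/dL against the printed label, and neither the eCRF field unit nor the derivation is shown. If values in g/L were compared with 2.5, the data are sound and only the table is wrong. If raw mg/dL numbers were compared with 2.5, everyone scores 0 and the high group is deflated: patients with truly low fibrinogen and 139 to 168 points on the other items would drop out of it. The documents also do not say whether sites or the database compute the total. This part of the objection stands in full.

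It is also fair that the implausibility of 2.5 g/dL rests on a laboratory range from outside the documents, and that the documents give no basis for a patient-level misclassification rate. Nor is this subgroup necessarily the only test of the biological rationale, since the protocol's Future additions section plans transcriptomic work on whether the treatment effect varies with leukocyte gene expression. Finally, HScore enters neither eligibility, randomization, the sample size nor the main model for the primary outcome.

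What the objection does not remove is the table itself. It is the named scoring key, not background text, and as printed it cannot do its job. That three plausible implementations give three different results, in a trial with 51 ICUs, is a reason to settle the unit.

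**Conclusion.** The concern holds in a limited form. The printed cut-off of 2.5 g/dL equals 25 g/L. Assuming fibrinogen between 100 and 1,500 mg/dL, literal use of Table 3 makes the item a constant 30 points and lowers the working threshold on the other items from 169 to 139. The documents do not establish whether the derived variable is inflated, deflated or correct, and they support no estimate of how many patients are affected.

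The reach is one row of Table 1S and one of nine subgroup interactions in Table 3S. The primary analysis, eligibility and sample size are unaffected. Severity is minor to moderate: a scoring rule that is wrong as written, behind a pre-specified subgroup, with no demonstrated effect on any main conclusion.

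**What to change.** 1. Confirm the fibrinogen unit against the HScore source cited in the protocol and against the eCRF field, then correct the Table 3 row. The item discriminates if 2.5 is in g/L (250 mg/dL), but the documents alone cannot confirm that this is the intended unit.
2. Assign a value of exactly 2.5 to one of the two categories, following the source, and state the ferritin unit.
3. Before Tables 1S and 3S are produced, document how HScore ≥ 169 was derived: who or what computed the total, and in which units.
4. Where raw laboratory values and units were captured, recompute the score centrally with the confirmed units. Where they were not, say so beside the baseline row and the subgroup result.

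The cost is one table correction, one check of the eCRF and, if the raw values exist, one scripted recalculation. Their availability is not assured: the blood sample rows of Table 1S list no fibrinogen, ferritin, triglyceride or AST, and the protocol mentions laboratory data only in general terms. No extra patients or study procedures are needed.
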